3.3. Sample size

Sample size requirements were calculated for the primary study outcomes using the Hayes and Bennet's formulas (16,17), using the following parameters: a 0.05 probability of a type I error, power of 0.90, and 48 clusters per treatment arm. Note that the power of 0.90 (higher than what is typically used) is used to minimize the risk of not detecting a program impact by underpowering the study. Adjustments were further made for intra-cluster correlation (since the study is cluster randomized). The outcome-specific intra-cluster correlation (ICC) coefficients are provided below. The estimated size of the eligible population in the 6 study upazilas was used to calculate the coefficient of variation of cluster sizes (equal to 0.424). We further assumed that baseline covariates provide a small amount of explanatory power of the study outcomes (correlation of 0.1).

We did not adjust the sample size for multiplicity (i.e., carrying out many comparisons). Our thinking is provided in Section 4.1.

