- **Stress of the pregnant woman:** Using an SD of 15.4 points (TMRI data), an ICC of 0.01 and the other parameters as defined above, we find that the study is powered to detect an impact on stress in women of 0.91 points (scale ranges from 0 to 40).
- **Stress of the husband of the pregnant woman:** Using an SD of 14.9 points (TMRI data), an ICC of 0.01 and the other parameters as defined above, we find that the study is powered to detect an impact on stress in women of 0.90 points (scale ranges from 0 to 40).
- **Maternal-fetal attachment:** Using a SD of 6 (39) and an ICC of 0.001, this sample size allows us to detect an effect of 0.83 for maternal-fetal attachment. This is equivalent to an effect size of 0.14.
- **Household food security:** Setting the prevalence of household food insecurity to 50% (the worst-case scenario in terms of power) and the ICC to 0.05 (equivalent to a design effect of 2.37), we can detect a change in the prevalence of food security of 10 percentage points. When the prevalence of food insecurity is 80%, the detectable difference is 8 to 9 percentage points.
- **Value of total household consumption:** Using an SD of 922 Tk (TMRI data), an ICC of 0.05 and the other parameters as defined above, we find that the study is powered to detect an impact on total per capita household food consumption of 193 Tk. Using an expected household size in the target population of 5 members, the effect we are able to detect is 965 Tk which is comparable to the size of the total transfer (1,000 Tk).
- **Value of household food consumption:** Using an SD of 621 Tk (TMRI data), an ICC of 0.05 and the other parameters as defined above, we find that the study are powered to detect an impact on total per capita household food consumption of 130 Tk. For an average 5-member household, the detectable difference are 650 Tk. We thus need to assume that at least 65% of the transfer are spent on food (top-up cash) or actually consumed by the household (food). This is a reasonable assumption, given that the BCC emphasizes the importance of using the transfers to improve the diet of the pregnant woman. In addition, TMRI households spent 62% of total expenditure on food.

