Birth length	-	-	Yes [#]
Birth head circumference	-	-	Yes [#]
Head circumference	-	-	Yes
MUAC	-	-	Yes
Infant length and weight	-	-	Yes
Colostrum intake, (exclusive) breastfeeding practices, infant and young feeding practices	-	-	Yes
Neonatal mortality	-	-	Yes
Household			
Value of non-food consumption	Yes	Yes	-
Housing quality	Yes	No	Yes
Asset ownership	Yes	No	Yes
Income from remittances		Yes	
Savings	Yes	Yes	Yes
Loans	Yes	Yes	Yes
Participation in other social security programs		Yes	
Additional outcomes			
Mother			
Height ^{&}	Yes	-	-
MCB program enrollment	Yes	Yes	Yes
Receipt of base cash	Yes	Yes	Yes
Receipt of food basket and top-up cash	Yes	Yes	Yes
Participation in BCC sessions	Yes	Yes	Yes
Husband			
Height ^{&}	Yes	-	-
Weight ^{&}	Yes	-	-
Participation in BCC sessions	Yes	Yes	Yes
Household			
Economic shocks	-	-	Yes

[#]These outcomes are assessed within 72 hours after birth.

* Maternal weight is also be measured during the census, i.e., before pregnancy

& Women's height and husband's height and weight are measured throughout the study period, i.e., when the team finds time to measure these outcomes.

Section 4 – Statistical principles

4.1. Level of statistical significance, confidence intervals to be reported, and adjustment for multiplicity

All statistical tests are two-sided. 95% confidence intervals are reported alongside exact p-values.

Multiplicity (i.e., carrying out many comparisons) has raised concerns about false-positive findings, which has led to recommendations to limit the number of comparisons made and/or to implement statistical adjustments. Multiplicity could arise in this trial in general for two reasons: having several outcomes of interest and having more than two study arms. We discuss both.

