6.1. Outcome definitions

The study includes three sets of outcomes: primary, secondary, and additional outcomes. The **primary study outcomes** are those outcomes that are predefined and for which the study is adequately powered to detect a feasible and meaningful effect (48).

The distribution of outcomes is inspected for normality and the variable transformed as necessary. More specific information on transformations is provided for key outcomes as needed.

- **Pregnant mother**

- **Gestational weekly weight gain 2nd to 3rd trimester:** Women's weekly weight gain (kg/wk) is calculated by differencing women's weight obtained in the 2nd and 3rd trimester and dividing by the number of weeks between both measurements.
- **Dietary energy intake and proportion of women below 85% of the estimate energy requirement (EER):** Dietary energy intake (kcal/day) is assessed using a 24hr recall in the second and third trimester (34). EER is calculated using each woman's basal metabolic rate (estimated from the woman's age, gender, and current weight), level of physical activity, and pregnancy trimester. Factors of 1.4 for low, 1.7 for moderate, and 2.0 for high physical activity is used (Food and Agricultural Organization, 2001). Additional energy requirement for the second and third trimester of pregnancy (340-350 kcal/d and 452-500 kcal/d, respectively, depending on which reference is used (35,36)) is added to account for gestational weight gain and increases in basal metabolic rate. Impact is assessed in the 2nd and 3rd trimester. Given continued advances in the analysis of 24h dietary recall data, the final analytic strategy to calculate the adequacy for each nutrient is based on recommended best practice at the time of the analyses.
- **Dietary protein intake:** The 24hr recall data is used to assess women's protein intake (g/day). Impact is assessed in the 2nd and 3rd trimester. Given continued advances in the analysis of 24h dietary recall data, the final analytic strategy to calculate the adequacy for each nutrient is based on recommended best practice at the time of the analyses.

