- **Prevalence of physical violence towards the pregnant woman/mother of the newborn child:** Prevalence of any physical intimate partner violence in the past 6 months, measured using the WHO Violence Against Women instrument (54). Impact is assessed in the 2nd and 3rd trimester of pregnancy and at 2 months (i.e., 61 days) postpartum.
- **Stress of the pregnant woman/mother of the newborn child:** Measured using women's Perceived Stress Scale score (55). Impact is assessed in the 2nd and 3rd trimester of pregnancy and at 2 months postpartum.
- **Maternal-fetal attachment:** Maternal attachment to their unborn child is assessed during their 3rd trimester of pregnancy using the Prenatal Attachment Inventory (56). In the Bangla translation of the Prenatal Attachment Inventory, all items in the scale were rephrased as questions instead of statements to make it easier for the interviewer to ask and to enhance the respondents' understanding.
- **Maternal-infant attachment:** Maternal attachment to their infant is assessed at 2 months (i.e., 61 days) postpartum using the Postpartum Bonding Questionnaire (57). The items in the Bangla-version of the scale were rephrased as questions instead of statements to simplify the interview process. Additionally, 2 of the 25 items in the original scale were removed. These 2 items (i.e., "I have done harmful things to my baby" and "I feel like hurting my baby") made up the subscale on Risk of Abuse and had low sensitivity (57). The sum of all items on the full scale, as well as each of the three subscales (Bonding, mother-infant relationship, and infant-focused anxiety), is used as outcome indicators.
- **Husband/partner of the pregnant woman:**
 - **Stress of the husband of the pregnant woman:** Measured using men's Perceived Stress Scale score (55). The second- and third-trimester assessment is used to assess impact.
- **Infant**
 - **Birthweight:** Birthweight (grams) is assessed within 72 hours after delivery to avoid the influence of transitory neonatal weight loss that typically happens during the first days of life.
 - **Low birthweight:** Low birthweight is defined as a birth weight below 2500 grams.
- **Household**

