 - **Household food security:** The Household Food Insecurity Access Scale is used to measure household food security status (58). The 2nd and 3rd trimester assessment is used to assess impact. Impact is assessed on the continuous scale (ranging from 0 to 27) and the categorical scale (food secure, mildly food insecure, moderately food insecure, or severely food insecure). The actual household groupings based on the categorical outcome depend on the population distribution.
 - **Value of total household consumption:** Aggregate value of household food and non-food consumption expenditures (Taka). This is a continuous measure calculated from household survey responses on consumption behavior, using the methodology and questionnaire modules described by Deaton and Zaidi (59). The 2nd and 3rd trimester assessment is used to assess impact. We assess inflation during the study period and deflate values as needed to be equivalent to the first wave in 2023. The distribution of this outcome is inspected for normality and the variable is transformed as necessary.

- **Value of household food consumption:** Value of household food consumption expenditures (Taka). This is a continuous measure calculated from household survey responses on consumption behavior, using the methodology and questionnaire modules described by Deaton and Zaidi (59). The 2nd and 3rd trimester assessment is used to assess impact. We assess inflation during the study period and deflate values as needed to be equivalent to the first wave in 2023. The distribution of this outcome is inspected for normality and the variable is transformed as necessary.

The **secondary study outcomes** are those outcomes on which the intervention is expected to have an impact but for which the study is unlikely to be adequately powered or for which statistical power cannot easily be calculated.

- **Pregnant mother**

- **Gestational weekly weight gain up to 2nd trimester:** Women's weekly weight gain (kg/wk) is calculated by differencing women's weight obtained at the census (before pregnancy) and 2nd trimester and dividing by gestational age in weeks.
- **Total gestational weight by the third trimester:** Total weight gain (kg) is calculated by calculating the difference between women's third trimester weight and the weight obtained at the time of the census.

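### Three primary outcomes carry two to four unranked indicators in SAP section 6.1, while section 3.3 gives one detectable effect for each

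*SAP*

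**What the plan says.** Section 6.1 sets two conditions for a primary outcome: it is predefined, and the trial has adequate power for a feasible and meaningful effect on it. Outcomes that are probably underpowered, or whose power is hard to calculate, are secondary. The same section then defines three primary outcomes by more than one indicator:

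- **Dietary energy.** The entry reads "Dietary energy intake and proportion of women below 85% of the estimate energy requirement (EER"), so it covers a mean intake and a proportion. Table 2 lists only energy intake.
- **Household food security.** Impact is assessed on the 0-27 score and on a four-level category. The SAP adds: "The actual household groupings based on the categorical outcome depend on the population distribution".
- **Maternal-infant attachment.** The outcome indicators are the sum of all items "as well as each of the three subscales", four in total.

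Section 3.3 gives one detectable effect for each: 174 kcal for energy, 0.65 points for attachment (SD 4), and 10 percentage points for food insecurity. The last is obtained by "Setting the prevalence of household food insecurity to 50% (the worst-case scenario in terms of power"), with 8 to 9 points at a prevalence of 80%.

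Section 4.1 makes no multiplicity adjustment for primary outcomes. Its stated reason is that each hypothesis is confined to one outcome.

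**The concern.** Nothing in the SAP ranks the indicators within these three outcomes or says how the food-security categories will be collapsed. Section 6.2 specifies linear mixed models for continuous and dichotomous outcomes and none for a four-level category, so some grouping is needed before the categorical result can be tested. That grouping defines the quantity tested.

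Two of the SAP's own statements then fail for these outcomes. The proportion below 85% of requirement, the 0-27 score and the subscales have no detectable effect in section 3.3, so they do not meet section 6.1's definition of primary. And the reason in section 4.1 for making no adjustment assumes one hypothesis per outcome, whereas here there are two to four.

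The SAP handles the same situation properly elsewhere. Length of gestation and preterm birth, and birthweight and low birthweight, are also continuous/binary pairs. Both members of each pair are in Table 2, the cuts are fixed (259 days, 2500 g), and each member has its own detectable difference.

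At stake is whether a claim on energy, food security or attachment rests on the result the trial was sized for.

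**Working it through.** **Inputs from the SAP.** Section 3.3: "a 0.05 probability of a type I error, power of 0.90, and 48 clusters per treatment arm"; "coefficient of variation of cluster sizes (equal to 0.424"); covariate "correlation of 0.1"; 1,152 women per arm (24 per cluster) in pregnancy; 816 per arm (17 per cluster) at 61 days; ICC 0.05 for energy and food security, 0.001 for attachment; SD 831 kcal and SD 4. Tests are two-sided (section 4.1).

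**Step 1: reproduce the stated effects.** Design effect DE = 1 + ((CV² + 1)m − 1) × ICC.

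- m = 24, ICC 0.05: 1 + (1.179776 × 24 − 1) × 0.05 = 2.37, as stated.
- m = 17, ICC 0.001: 1 + (1.179776 × 17 − 1) × 0.001 = 1.019.

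Detectable mean difference = (1.960 + 1.282) × SD × √(2 × DE × (1 − 0.1²)/n).

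- Energy: 3.242 × 831 × √(2 × 2.366 × 0.99/1,152) = 172 kcal; 174 with t quantiles on 94 df. Stated: 174.
- Attachment: 3.242 × 4 × √(2 × 1.019 × 0.99/816) = 0.645; 0.652 with t quantiles. Stated: 0.65.

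For food insecurity, the effective n per arm is 1,152/(2.366 × 0.99) ≈ 492. Solving the two-proportion power formula for 90% gives:

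- at 50%: 10.3 points (stated 10);
- at 80%: 7.6 points upward, 8.9 downward (stated 8 to 9).

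The stated figures reproduce, each for one indicator only.

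**Step 2: what the open grouping does to the detectable effect.** Same formula, detectable reduction by the share of households above the cut:

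| Share above cut | Points | Relative reduction |
|---|---|---|
| 20% | 7.6 | 38% |
| 30% | 9.0 | 30% |
| 50% | 10.3 | 21% |
| 80% | 8.9 | 11% |

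In absolute terms 50% is indeed the least favourable. In relative terms the target varies more than threefold, so whether it is feasible cannot be judged until the grouping is known.

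**Step 3: type I error if any significant indicator were claimed.** Per arm contrast, per visit, nominal 5%. Independence is the upper reference: 1 − 0.95² = 9.75% for two indicators and 1 − 0.95⁴ = 18.5% for four. The indicators are correlated, so the realistic figures are lower. The documents give no correlations; those below are assumptions.

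- **Food security, score plus one fixed cut:** about 8%. A normal latent score cut at its median correlates 0.80 with the dichotomy and gives 7.8%.
- **Food security, most significant of three cuts:** 12.2% by simulation (null over-dispersed 0-27 count, 1,152 per arm without clustering, 4,000 replicates, assumed cuts at >1, >4 and >8).
- **Food security, cut nearest 50% in the pooled data, arm ignored:** 4.7% in the same simulation, i.e. no inflation.
- **Attachment, total or any of three equally correlated subscales:** 14.4%, 12.9% and 11.1% at subscale correlations 0.3, 0.5 and 0.7.
- **Energy, kcal plus proportion below 85% of requirement:** about 8%, taking the 28% prevalence from the dietary survey of 600 pregnant women in section 2.1 and a normal latent intake.

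With one deciding indicator, each contrast returns to 5%.

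**The case against.** A reader might infer that the food-security rule itself costs 12%. The SAP does not support that. It ties the grouping to a distribution, not to the difference between arms, and a cut chosen on pooled data without regard to arm leaves the error near 5%. The 12% needs someone to try several cuts and keep the most significant. The SAP neither says the choice will be pooled and blind to arm nor suggests the opposite, so 12% is a worst case. That the trial is unmasked does not settle how the grouping will be chosen.

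A reader might also infer that the stated detectable effects belong to no reported indicator, or that nothing about these outcomes is fixed. Neither holds. 174 kcal belongs to kcal/day, which is reported. 0.65 most likely belongs to the full attachment scale, although section 3.3 does not name it. The 10 points belong to a food-insecurity prevalence at the least favourable absolute value. The four category names are listed in advance; only their grouping is open. For energy, Table 2 and section 3.3 both point to kcal/day, and the 85% threshold is prespecified, so this is the mildest of the three.

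Finally, the SAP nowhere says that one significant indicator would count as success, and it commits to reporting confidence intervals and exact p-values, so selective emphasis would be partly visible. All of this limits the size of the problem. What stands is that the SAP does not state which indicator decides or how the categories will be grouped, and that its own definition and its own reason for no adjustment require it to.

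**Conclusion.** The point holds as an inconsistency within the SAP. Energy and food security have two unranked indicators each (more for food security, depending on the grouping), attachment has four, and section 3.3 sizes one per outcome.

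The potential cost per contrast and visit is a type I error of about 8% for energy and for food security with one fixed cut, and about 11 to 14% for attachment, against a nominal 5%. These figures assume that any significant indicator would be claimed, and they rest on assumed correlations and distributions. They do not count the two arm contrasts, or the two visits at which energy and food security are assessed.

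The sample size calculation is sound for the indicators it covers. The change should be made before the outcome data are analysed, but it does not call the design into question.

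**What to change.** In section 6.1, name as deciding the indicator that section 3.3 already powers:

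- **Energy:** intake in kcal/day.
- **Attachment:** the full-scale sum, with section 3.3 stating that SD 4 refers to it.
- **Food security:** one prevalence of food insecurity, with the dichotomy fixed now from the four listed categories (for example, food secure versus any food insecurity) instead of from the trial's own distribution.

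Move the proportion below 85% of requirement, the three subscales, the 0-27 score and any other food-security groupings to secondary, where section 6.1 already places outcomes without a power calculation.

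If the sponsor prefers the 0-27 score as deciding, that is equally acceptable, provided that its detectable effect is added to section 3.3 (about 0.21 SD: 3.242 × √(2 × 2.366 × 0.99/1,152) = 0.207, or 0.209 with t quantiles, at ICC 0.05) and the prevalence moves to secondary.

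The cost is SAP wording; data collection and sample size are unaffected. A few indicators lose primary status. Because the SAP tracks its departures from the trial registration, this change must be reconciled with that record as well.

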3.1. Trial design

A three-arm cluster-randomized, non-blinded, community-based, mixed cross-sectional and longitudinal trial is used to estimate the effectiveness of the intervention. The unit of randomization is a grouping of 3 wards³. Each ward group is randomly assigned to one of three study groups, all of which receive the improved maternity allowance program:

- **Arm 1 – “standard” package, i.e., base cash and nutrition behavior change communication (BCC):** pregnant women receive 800 BDT each month and group-based BCC on nutrition with a focus on how to improve their dietary intake during pregnancy.
- **Arm 2 – “standard” package + food basket:** pregnant women in this arm receive the base cash of 800 BDT each month, group-based BCC, and in addition a monthly food basket composed of rice, lentils, and oil valued at approximately 1,000 BDT.
- **Arm 3 – “standard” package + top-up cash:** pregnant women in this arm receive the base cash of 800 BDT each month, group-based BCC, and in addition receive a monthly additional cash transfer of 1,000 BDT instead of the food basket.

The study is a hybrid of a cross-sectional and longitudinal design. It follows women from their second trimester of pregnancy to around 2 months after childbirth. A census is conducted to identify households with women who met the program’s eligibility criteria (see Section 5.2). The study then uses a total of 6 three-month long data collection waves. Women in the 2nd trimester of pregnancy (based on self-reported last menstrual period⁴ and ultrasound reports and antenatal care cards when available) were enrolled in the study in the first four waves (Figure 1). Household and individual data are collected at enrollment. In the wave following enrollment, data are collected on the same women who are now in the 3rd trimester. Third trimester data collection is conducted at around 34 weeks of gestation (± 1 week). Subsequent waves are used to assess newborn weight and length (collected within 72 hours after child birth) and to assess anthropometric and other outcomes at around 2 months postpartum (61 days ± 1 week). In the final follow-up round (1 month in length), women in the 3rd trimester of pregnancy not captured in wave 5 are surveyed. In addition, the newborn survey is conducted. The number of survey rounds is based on the sample size calculations presented below and field reports regarding the actual number of study subjects enrolled and successfully followed up.

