³ The administrative structure in Bangladesh consists of divisions (8), districts (64), subdistricts or upazilas (491), and unions. Up to about 15 years ago, each union consisted of 3 wards. Since then, the ward system was changed to 9 wards per union, each identified by a number (i.e., from 1 to 9). The study uses the old definition of wards (i.e., 3 per union) as the unit of randomization.

⁴ Pregnancy trimesters are defined as follows: 1st trimester: 2 to 13 weeks of pregnancy (meaning, weeks since first day of the last menstrual period); 2nd trimester: 14 to 26 weeks of pregnancy; 3rd trimester: 27 weeks of pregnancy until delivery.

[figure not shown]

Figure 1: Study design (note: dates are approximate)

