- **Use of iron-folic acid, and calcium, and vitamin B complex, and multiple micronutrient supplements¹²:** Women are asked to report on their use of these supplements during pregnancy. The 2nd and 3rd trimester assessment is used to assess impact. We report on % of women who ever consumed these supplements during this pregnancy, the % who consumed the supplement in the past 7 d, and the frequency of consumption in the past 7d.
- **Antenatal care utilization:** Antenatal care utilization is assessed using a variety of measures based on current recommendations in Bangladesh and the new WHO guidelines (60). The 2nd and 3rd trimester and postpartum¹³ assessment is used to assess impact.
- **Prenatal nutrition knowledge:** Women's knowledge related to nutrition is assessed using a set of questions developed for this study. The 2nd and 3rd trimester assessment is used to assess impact. The construction of the outcome measure(s) is based on the distribution of and the association between the variables on which data were collected.
- **Postnatal care utilization:** Postnatal care utilization is assessed using a variety of measures based on current recommendations in Bangladesh and WHO guidelines. The 2-month postpartum assessment is used to assess impact.
- **Postpartum weight:** We measure women's weight (kg) at the 2-month postpartum visit.
- **Spousal relationship between the pregnant woman/mother of the newborn child and her husband:** Measured using women's spousal relationship modules developed for the survey. Impact is assessed in the 2nd and 3rd trimester of pregnancy and at 2 months postpartum. The construction of the outcome measure(s) is based on the distribution of and the association between the variables on which data were collected.
- **Decision making by the pregnant woman/mother of the newborn child:** Measured using women's decision-making modules adapted from pro-WEAI (61). Impact is assessed in the 2nd and 3rd trimester of pregnancy and at 2 months postpartum. The construction of the outcome

¹² The trial registration includes vitamin B complex supplementations. Since these vitamin supplements are not part of the Bangladesh National Strategy for Maternal Health, we dropped questions about vitamin B complex supplement use from the survey.

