¹³ The trial registration incorrectly limits this outcome to the 2nd and 3rd trimester observations. Data were collected on this outcome postpartum as well and this information is used to assess impact on this outcome for the entire pregnancy.

measure(s) is based on the distribution of and the association between the variables on which data were collected.

- **Mobility of the pregnant woman:** Measured using mobility modules adapted from pro-WEAI (61). Impact is assessed in the 2nd and 3rd trimester of pregnancy and at 2 months postpartum. The construction of the outcome measure(s) is based on the distribution of and the association between the variables on which data were collected.
- **Labor force participation of the pregnant woman:** Measured using women's labor modules developed for the survey. The 2nd and 3rd trimester assessment is used to assess impact. The construction of the outcome measure(s) is based on the distribution of and the association between the variables on which data were collected.
- **Attitudes toward gender and intimate partner violence of the pregnant woman:** Measured using women's attitudes toward gender and intimate partner violence modules developed for the survey. Impact is assessed in the 2nd and 3rd trimester of pregnancy and at 2 months postpartum. The construction of the outcome measure(s) is based on the distribution of and the association between the variables on which data were collected.
- **Social capital of the pregnant woman:** Measured using modules on women's social interactions and perceptions of neighborhood responses to intimate partner violence, developed for the survey. Impact is assessed in the 2nd and 3rd trimester of pregnancy and at 2 months postpartum. The construction of the outcome measure(s) is based on the distribution of and the association between the variables on which data were collected.
- **Agency of the pregnant woman:** Measured using women's responses on locus of control (62). Impact is assessed in the 2nd and 3rd trimester of pregnancy and at 2 months postpartum. The construction of the outcome measure(s) is based on the distribution of and the association between the variables on which data were collected.

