Even though randomization should yield equivalence between arms on covariates, we include covariates or make other adjustments (such as re-weighting) in case of non-equivalence of enrollment measures or due to differential attrition. In addition, we include covariates (tentative list in Table 4) that are orthogonal to the randomized treatment assignment and are known or suspected predictors of the outcome of interest (such as, maternal age and education) to reduce residual noise (i.e., increase statistical power). A tentative list of covariates is presented in Table 4. Decisions on which covariates to ultimately include is based on factors such as the extent to which potential covariates are correlated with outcomes, the share of observations with missing values of potential covariates, and the extent to which potential covariates have realistic distributions.

Table 4: Tentative list of covariates to be included in regression models

Outcome	Covariates
All outcomes	Socio-economic status (using census data), upazila, woman's educational attainment, woman's age, season, having an NID
Dietary outcomes	Additional covariates: Interviewer, day of week
Prevalence of emotional violence, controlling behaviors, physical violence, stress	Additional covariates: partner's age, partner's educational attainment, woman's gestational age
Attachment	Additional covariates: -
Birth outcomes	Additional covariates: Maternal height, maternal BMI at census, primiparity, child sex
Household food security, value of household consumption	Household adult equivalents

Distributional assumptions for outcome variables is checked using descriptive statistics. Transformations are used for continuous outcome variables if needed to obtain more symmetric distributions.

In addition to the models described above, we conduct robustness checks by estimating fixed effects models.

The intent to treat analyses do not include any subgroup analyses (e.g., by maternal age, season, etc.)

Modified intent to treat analysis

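### At the 2nd-trimester round, ever-use of supplements and any cumulative antenatal care measure depend on weeks of pregnancy at interview, which Table 4 does not list for these outcomes

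*SAP*

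**What the plan says.** **Outcomes (Section 6.1, secondary outcomes).** Supplement use has three measures. One is cumulative: "We report on % of women who ever consumed these supplements during this pregnancy". The other two are not: "the % who consumed the supplement in the past 7 d, and the frequency of consumption in the past 7d". All are assessed in the 2nd and 3rd trimester. For antenatal care the measures are left open: "Antenatal care utilization is assessed using a variety of measures based on current recommendations in Bangladesh and the new WHO guidelines". They are assessed in both trimesters and postpartum. Footnote 13 says of the postpartum data that "this information is used to assess impact on this outcome for the entire pregnancy". Table 2 does not mark a postpartum assessment for antenatal care; I follow Section 6.1 and its footnote, which are explicit.

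**Timing (Section 3.1).** Footnote 4 gives the first window: "2nd trimester: 14 to 26 weeks of pregnancy". The second is narrow: "Third trimester data collection is conducted at around 34 weeks of gestation (± 1 week".

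**Covariates (Section 6.2, Table 4).** The row for all outcomes reads "Socio-economic status (using census data), upazila, woman's educational attainment, woman's age, season, having an NID". Gestational age appears only in the row for violence, controlling behaviors and stress: "Additional covariates: partner's age, partner's educational attainment, woman's gestational age". Supplement use and antenatal care have no row of their own. The SAP calls the table tentative. It also allows covariates or re-weighting if the arms prove unequal at enrollment. Table 3 gives gestational age at enrollment as an example of a characteristic to be shown by arm.

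**The concern.** A woman interviewed at 26 weeks has had 26/14 = 1.86 times the pregnancy time of one interviewed at 14 weeks. Whether she has ever taken a supplement, or how many visits she has made, therefore depends partly on when the interviewer came. Model (2) represents time by survey round, and round does not absorb week-to-week differences within the 2nd trimester. Because arm is interacted with round, the 2nd-trimester contrast would carry any arm difference in timing in full.

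The SAP handles this elsewhere. It divides weight gain up to the 2nd trimester by weeks of gestation. It also lists gestational age for the violence outcomes, which use a fixed six-month recall and so depend less directly on elapsed pregnancy time than an ever-use measure does.

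Two things are at stake: some avoidable residual variance and, if interview timing differed systematically between arms, a spurious effect on care or supplement use.

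**Working it through.** The SAP states no rate, power or detectable difference for these outcomes, so there is no figure of its own to reproduce. What follows is an illustration.

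**Inputs from the SAP.** 1,286 women enrolled per arm, 48 clusters per arm, coefficient of variation of cluster size 0.424, two-sided alpha 0.05, power 0.90 (Sections 3.3 and 4.1). The intra-cluster correlation of 0.01 is borrowed from gestational weight gain.

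**Assumptions not in the SAP.** Interviews are spread evenly over weeks 14 to 26. Ever-use rises linearly over those weeks by 20, 40 or 60 points around a mean of 60% (50 to 70%, 40 to 80%, 30 to 90%).

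**1. Spread of timing.** Even over weeks 14 to 26: variance 14, SD 3.7 weeks. Even over weeks 33 to 35: SD 0.8 week. The issue is essentially confined to the 2nd-trimester round.

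**2. Design effect.** 1 + ((CV² + 1)m − 1) × ICC, with m = 1,286/48 = 26.8, gives 1 + (1.180 × 26.8 − 1) × 0.01 = 1.306. As a check, with m = 24 and ICC 0.05 the formula gives the SAP's 2.37. With m = 24 and ICC 0.01 it gives 1.27, where the SAP states 1.35. Using 1.35 here would move the detectable difference below only from 7.16 to about 7.28 points.

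**3. Unadjusted detectable difference.** SE = √(2 × 0.6 × 0.4 × 1.306 / 1,286) = 2.21 points. Multiplying by (1.960 + 1.282) gives 7.16 points.

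**4. Variance explained and gain from adjusting.** Slope = rise/12. Share explained = slope² × 14 / 0.24. Adjusted detectable difference = 7.16 × √(1 − share).

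| Assumed rise | Slope per week | Variance explained | Detectable difference |
|---|---|---|---|
| 20 points | 1.7 points | 1.6% | 7.16 → 7.10 |
| 40 points | 3.3 points | 6.5% | 7.16 → 6.92 |
| 60 points | 5.0 points | 14.6% | 7.16 → 6.61 |

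For a visit count, assumed Poisson and accruing from week 8 at 0.1 to 0.2 visits per week, the same reasoning gives about 10 to 19% of variance.

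**5. Systematic timing difference.** Bias = slope × weeks of difference between arms. With no true effect, the two-sided rejection rate is P(|Z| > 1.96) for Z normal with mean bias/SE and unit variance.

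| Assumed rise | Half-week difference: bias, type I error | One-week difference: bias, type I error |
|---|---|---|
| 20 points | 0.8 points, 0.07 | 1.7 points, 0.12 |
| 40 points | 1.7 points, 0.12 | 3.3 points, 0.33 |
| 60 points | 2.5 points, 0.21 | 5.0 points, 0.62 |

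**6. Chance difference.** With the same design effect, the SD of the arm difference in mean timing is √(2 × 14 × 1.306 / 1,286) = 0.17 week, worth about 0.3 to 0.8 point. This is ordinary sampling variation already contained in the standard error. It does not bias the test.

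**The case against.** The strongest reply is that Table 4 is not a final specification. The SAP calls it tentative and intends to include known or suspected predictors of each outcome, which gestational age at interview plainly is for a cumulative measure. The specific rows mainly serve primary outcomes, so its absence here is not a decision to exclude it. Gestational age at enrollment is already an example in the by-arm table, and enrollment is the 2nd-trimester survey, so an imbalance would be visible and Section 6.2 would allow a response. All of this stands. What remains is that the response is discretionary, has no threshold, and would be chosen after the data are seen.

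A reader might infer that all supplement and antenatal care results are exposed. The SAP does not support that. Two of the three supplement measures use a seven-day recall, the later survey is nearly fixed in gestation, and the postpartum data cover the whole pregnancy. Nor does the SAP say that every antenatal care measure is cumulative.

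A reader might also infer bias from the fact that women are enrolled after unmasked assignment, up to a quota (Sections 3.2 and 5.1). That is a possible route only. The same visiting procedure is described for all arms, and no passage shows that timing differs between them.

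**Conclusion.** The point holds in a narrow form. At the 2nd-trimester round, ever-use of supplements and any cumulative antenatal care measure depend on gestational age at interview, and the listed covariates do not include it for these outcomes.

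The expected cost is a small loss of precision: for ever-use, about 1.6 to 14.6% of outcome variance and at most about 0.55 point in detectable difference. A bias of about 1.7 to 5 points per week would arise only with a systematic arm difference in timing that went unadjusted. These sizes rest on the assumed rises, the even spread of interviews and the borrowed intra-cluster correlation. The textual finding does not depend on them. As the outcomes are secondary and the effect is modest, this is an improvement worth making rather than a flaw that threatens the trial's conclusions.

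**What to change.** In Table 4, add a row for ever-use of supplements and cumulative antenatal care measures, with gestational age at interview as a prespecified covariate for the 2nd-trimester assessment. In model (2), give it a round-specific slope. State which antenatal care measures count as cumulative. Keep gestational age at enrollment in the by-arm table as a firm entry rather than an example.

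The cost is a few lines of SAP text; gestational age at enrollment is already among the characteristics to be summarized, so no new data are needed. One caveat should be written down. Section 3.1 dates pregnancies from the reported last menstrual period, and from ultrasound reports and antenatal care cards where these exist, so the accuracy of the covariate may itself depend on care use. That is a reason to describe the dating source, not to leave the covariate out.
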